A total of 111 hospitalized DM2 patients not critical to the study were evaluated. Of these, 35 did not meet the inclusion criteria and the 76 included participants were randomized into two groups. The recruitment of patients began on November 15, 2017 and ended on June 1, 2018. The "physiological" insulin group with 37 participants and the traditional group with 39 participants. Within the "physiological" group, 1 patient was eliminated before initiating the insulin regimen, presenting acute abdomen and requiring intensive therapy. Therefore, 36 patients in the "physiological" group and 39 patients in the traditional group began treatment, who entered the analysis for intention to treat. From the physiological group 6 patients did not conclude the treatment by discharge before the control and 2 patients due to poor adherence to the treatment. In the traditional group, 5 patients withdrew before the control, 1 patient due to poor adherence to treatment, 1 patient died before the control, and 1 patient was suspended due to critical condition. At the end of the study, 28 patients in the "physiological" group and 31 patients in the traditional group were completed in the analysis per protocol. In 20 (71.4%) patients in the first group and in 30 (96.8%) patients in the second group, treatment was completed until discharge.

POPULATION CHARACTERISTICS

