Of the total patients analyzed for intention to treat, 34 (45.3%) patients were men and 41 (54.7%) women. According to the place of hospitalization, 18 (24%) were in the internal medicine service, 29 (38.7%) in traumatology and orthopedics and 28 (37.3%) in general surgery. The mean age of the patients was 57.83 ± 13 years. The average body mass index was 26 ± 5.1 kg / m². The mean random glucose at admission was 230.5 ± 70.2 mg / dL, the glycosylated hemoglobin level was $8.3 \pm 2.3\%$, and the serum creatinine was 1 ± 0.5 mg / dL. The treatment before admission was with oral hypoglycemic agents in 25 (33.3%) patients, with insulin in 25 (33.3%) patients, the combination of oral hypoglycemic agents and insulin in 12 (16%) patients and 13 (17.3%) patients. they received treatment or were diagnosed at the time of admission. The average dose of insulin administered was 29.6 ± 11.6 IU and the number of days of hospital stay was 9.3 ± 5 days. The reasons for admission to the hospital were: abscesses and soft tissue infection, hip fracture, diabetic foot, other fractures, cancer, heart disease, gastrointestinal bleeding, acute cholecystitis, stage IV chronic kidney disease, pneumonia, gonarthrosis, pathway infection urinary tract, intoxications, meningitis, alveolar obesity-hypoventilation syndrome, peripheral thrombosis and obstructive uropathy.

EFFECTIVENESS RESULTS

When evaluating efficacy, by protocol, the following was observed: The fasting glucose average in the "physiological" group was 130.3 ± 20.9 mg / dl, while in the traditional group it was 126 ± 22 mg / dl ($p = 0.114$); the average postprandial glucose in the physiological group was 150.8 ± 22.8 mg / dl and in the traditional group it was 149.4 ± 28.1 mg / dl ($p = 0.833$). The average morning glucose in the first group was 130.9 ± 18.3 mg / dl and 125.9 ± 26.7 mg / dl in the second group ($p = 0.081$).

In the analysis by intent to treat in the same way control was achieved in goals in both groups. The average fasting glucose in the "physiological" group was 135 ± 22.6 mg / dl, while in the traditional group it was 129.6 ± 23.6 mg / dl ($p = 0.114$); the average postprandial glucose in the physiological group was 156.2 ± 27.2 mg / dl and in the traditional group it was 155.4 ± 29 mg / dl ($p = 0.902$). The average morning glucose in the first group was 136.2 ± 21.2 mg / dl and 127.4 ± 26.6 mg / dl in the second group ($p = 0.081$).

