The number of days to reach control during the hospital stay statistically were not different between groups (by protocol 4.9 ± 2.2 days vs 4.7 ± 2.4 days, $p = 0.553$, by intention to treat 4.9 ± 2.1 days vs 4.7 ± 2.3 days, $p = 0.445$).

SAFETY RESULTS

Safety was evaluated with episodes of hypoglycemia and complications associated with diabetes. In the "physiological" group it was observed that 15 (41.6%) patients had at least one event of hypoglycemia during their entire stay; On the other hand, in the traditional group 15 (38.4%) presented at least one event of hypoglycemia (per protocol, RR: 1.11, 95% CI: 0.62 to 1.97, $p = 0.729$; intention to treat, RR = 1.08, 95% CI: 0.62 to 1.89, $p = 0.777$). The presence of more than 2 hypoglycemic events during their hospitalization was observed in 8 (22.2%) patients of the "physiological" group and in 2 (5.1%) patients of the traditional group (per protocol, RR = 7.75, 95% CI: 1.02 a 59.13, $p = 0.021$; by intention to treat, RR: 4.33, 95% CI: 0.98 to 19.07, $p = 0.041$).

In the analysis by protocol, the rate of the number of total events / patients with hypoglycemia in the "physiological" group was 2.4 ± 1.3 events / patient, while in the traditional group it was 1.6 ± 0.7 events / patient ($p = 0.129$) ; in the intention-to-treat analysis in the "physiological" group it was 2.5 ± 1.6 events / patient, whereas in the traditional group it was 1.7 ± 0.9 events / patient ($p = 0.182$).

Thirty-eight hypoglycemic events were found in the "physiological" group and 26 hypoglycemic events in the traditional group; of which, 36 were mild hypoglycemia in the "physiological" group and 24 events in the traditional group (RR per protocol: 1.02, 95% CI: 0.91 to 1.19, $p = 1.0$; RR by intention to treat: 1.03, 95% CI: 0.90 to 1.17, $p = 1.0$).

Regarding the complications associated with diabetes, soft tissue infection was the most frequent, one patient had pneumonia, one acute renal failure, one acute

respiratory failure, and no patient presented bacteremia, diabetic ketoacidosis or hyperosmolar state. Two of the patients included in the study died from complications not associated with hypoglycemia, one in the physiological group secondary to progression of the infectious process, sepsis and septic shock, and one in the group Traditionally associated with acute respiratory failure.

SECONDARY RESULTS

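### Two hypoglycaemia comparisons labelled intention to treat leave out the event-free patients: one averages over the 15 + 15 patients with an event, and the other (mild RR 1.03) is a share of events

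*Combined protocol and SAP*

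**What the plan says.** Patients of the Study defines the intention-to-treat set: 36 physiological patients and "39 patients in the traditional group began treatment, who entered the analysis for intention to treat". One of the 37 patients randomised to the physiological scheme never started it.

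Safety Results then gives four hypoglycaemia comparisons described as intention to treat:

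- At least one event: 15 patients in each arm, RR 1.08 (0.62 to 1.89). The count covers "patients had at least one event of hypoglycemia during their entire stay".
- More than 2 events: 8 vs 2 patients, RR 4.33 (0.98 to 19.07).
- Events per patient, defined as "the rate of the number of total events / patients with hypoglycemia": 2.5 ± 1.6 vs 1.7 ± 0.9, p = 0.182.
- Mild hypoglycaemia: 36 of 38 events vs 24 of 26 events, reported as "RR by intention to treat: 1.03, 95% CI: 0.90 to 1.17, $p = 1.0". No denominator is named for this ratio.

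Hospital stay appears only for both arms together, under Population Characteristics: "the number of days of hospital stay was 9.3 ± 5 days".

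**The concern.** Whether a patient has any hypoglycaemia is an outcome of the assigned scheme. A comparison restricted to patients who had it no longer compares the groups that randomisation formed, and attaching a p-value and an intention-to-treat label does not restore that.

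The mild ratio has a different fault. It describes the severity mix among events. If one scheme doubled mild and other events alike, the ratio would still be 1.0. It also treats repeat events in one patient as independent, although 64 events came from 30 patients. A reader who meets an intention-to-treat RR of 1.03 with p = 1.0 can easily conclude that mild hypoglycaemia was equally frequent in the two arms, which the figure cannot show.

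The sample size was based on the rate of hypoglycaemia, so these lines concern the outcome on which the trial was planned. No event rate over all treated patients is given with an interval.

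**Working it through.** **Inputs** (Patients of the Study; Safety Results): treated patients 36 and 39; patients with an event 15 and 15; events 38 and 26; mild events 36 and 24; patients with more than 2 events 8 and 2; SDs 1.6 and 0.9. The physiological arm comes first throughout.

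**1. Reproducing the events-per-patient line.** 38/15 = 2.53 and 26/15 = 1.73, which match the printed 2.5 and 1.7. Over all treated patients those means would need 2.5 × 36 = 90 and 1.7 × 39 = 66 events. The denominator is therefore the 30 patients with an event, and 75 − 30 = 45 are omitted.

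**2. Reproducing the mild RR.** (36/38)/(24/26) = 0.947/0.923 = 1.026. SE of log RR = √(1/36 − 1/38 + 1/24 − 1/26) = 0.0683, so the 95% CI is 0.898 to 1.173; Fisher p = 1.0. All four printed values match. A search of every whole-number split of 36 and 39, 37 and 39, or 15 and 15 patients finds none that gives 1.03 (0.90 to 1.17). The unit is the event.

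**3. The other two lines.** (15/36)/(15/39) = 1.083 (0.62 to 1.89) and (8/36)/(2/39) = 4.33 (0.98 to 19.07). Both reproduce on 36 and 39 patients and are not affected.

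**4. Rates over all treated patients.**

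| | Physiological | Traditional | Ratio | Poisson 95% CI |
|---|---|---|---|---|
| All events | 38/36 = 1.06 | 26/39 = 0.67 | 1.58 | 0.96 to 2.61 |
| Mild events | 36/36 = 1.00 | 24/39 = 0.62 | 1.63 | 0.97 to 2.72 |

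The Poisson intervals use SE = √(1/38 + 1/26) = 0.255 and √(1/36 + 1/24) = 0.264. They ignore repeat events within a patient and are too narrow. The all-event ratio splits into 1.083 (patients with any event) × 1.462 (2.53/1.73, events among those patients) = 1.58. With all 37 randomised, and no events assumed for the patient who never started, it is 1.54 (Poisson 0.94 to 2.54).

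**5. Allowing for repeat events.** The intention-to-treat totals, SDs and more-than-2 counts leave 8 possible sets of patient counts in the physiological arm and 1 in the traditional arm. With 21 and 24 zeros added, robust-SE Poisson intervals for 1.58 run from about 0.80 to 3.1 (p 0.18 to 0.19) and negative binomial intervals from about 0.74 to 3.4 in all 8. The printed per-protocol figures cut the 8 sets to 2. One of those 2 gives Mann-Whitney p-values (no continuity correction) of 0.182 on the 15 + 15 patients and 0.129 per protocol, the two printed values. This is further evidence that zeros were left out.

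For mild events, patient-level counts cannot be recovered. The all-patient SDs implied by the printed figures are 1.62 and 1.01, so the relative SE for all events is √(1.62²/(36 × 1.056²) + 1.01²/(39 × 0.667²)) = 0.353. Assuming the same value for mild events, the interval is 1.625 × exp(± 1.96 × 0.353) = 0.81 to 3.25.

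**6. Time at risk.** Stay by arm is not given, so the per-day ratio is unknown. As an illustration only, hold the pooled mean at 9.3 days and let the arm means differ by up to 3 days. Stays of 10.86 vs 7.86 days give 1.583 × 7.86/10.86 = 1.15; stays of 7.74 vs 10.74 days give 1.583 × 10.74/7.74 = 2.20.

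**7. Per protocol.** The same form appears. RR 1.11 (0.62 to 1.97) implies 13/28 vs 13/31, and means of 2.4 and 1.6 then imply 31 and 21 events. These counts are inferred. They give an all-patient ratio of (31/28)/(21/31) = 1.63 (Poisson 0.94 to 2.84). A mild share of (30/31)/(20/21) = 1.016 (0.91 to 1.14) agrees with the printed 1.02 and lower limit 0.91, but not with the printed upper limit 1.19.

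**The case against.** The first measure names its denominator openly, and the intention-to-treat label could be read as saying only which population the 15 + 15 patients came from. The mild ratio follows directly after the event counts, so a careful reader can see that it is a share of events, and nowhere does the document claim equal mild-event frequency. The safety signal is not hidden either: more than 2 events (RR 4.33) and suspension or change of scheme (8 vs 1, RR 8.67) are reported on the treated patients, and the raw event totals are printed. Finally, every recomputed interval includes 1.

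Much of this stands. It limits the weight of the point: the fault lies in two labelled comparisons, and the overall reading on safety does not turn on them. But naming the subset does not make a p-value within it a comparison of the treatment groups, and the mild RR states no denominator at all. It is also fair that the simple Poisson intervals look nearer to significance than they should, so the conclusion below rests on the intervals that allow for repeat events. Hospital stay is itself measured after randomisation, so a rate per day should not stand alone.

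**Conclusion.** The concern holds. Neither the events-per-patient line nor the mild RR is an intention-to-treat comparison as the document defines that set. Over the 36 + 39 treated patients, the all-event ratio is 1.58, with a 95% CI of about 0.80 to 3.1 (robust Poisson) or 0.74 to 3.4 (negative binomial). The mild-event ratio is 1.63, about 0.81 to 3.25 on the assumption that its relative SE equals that for all events. What changes is the message on mild events: from 1.03 with a tight interval, suggesting equality, to about 1.6 with a wide one, which is uncertainty. A higher rate with the physiological scheme is not shown. The point estimates follow directly from printed counts; the robust intervals for all events rest on patient counts reconstructed from the printed totals and SDs. None of these figures allows for days at risk, which the document does not give by arm.

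**What to change.** - Analyse the number of events per patient, zeros included, in the 36 + 39 treated patients, with a negative binomial or robust-SE Poisson model. Report the rate ratio and 95% CI for all events and for mild events.
- Use log hospital days at risk as the offset, and show the per-patient ratio without an offset beside it. Do not use days on the scheme: suspension for hypoglycaemia shortens them, while patients with an event are counted over the whole stay. Report stay by arm.
- Add a sensitivity analysis on all 37 + 39 randomised if follow-up days exist for the patient who never started.
- Relabel 36/38 vs 24/26 as the proportion of events that were mild, with an interval clustered by patient and no between-scheme test, or drop it.
- Present 2.5 vs 1.7 as descriptive, among patients with an event, without the intention-to-treat label. Treat the per-protocol counterparts alike, and check the printed upper limit of 1.19.

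The cost is a few relabelled lines and one short re-analysis. The patient-level counts must already exist, since SDs were computed from them. The drawback is a visibly wide interval; the finding of no significant difference in total events is unlikely to change.

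### Complications associated with diabetes, a named safety outcome, are reported pooled over arms, without an onset rule and with inconsistent listing, so they support no between-arm statement

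*Combined protocol and SAP*

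**What the plan says.** The Safety results section opens by naming two outcomes: "Safety was evaluated with episodes of hypoglycemia and complications associated with diabetes". Hypoglycemia is then given by arm with a risk ratio, a 95% CI and a p value.

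Complications get one sentence: "Regarding the complications associated with diabetes, soft tissue infection was the most frequent, one patient had pneumonia, one acute renal failure", and then one acute "respiratory failure, and no patient presented bacteremia, diabetic ketoacidosis or hyperosmolar state". The sentence names no arm and no denominator, and gives no number for soft tissue infection.

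The next sentence turns to deaths: "Two of the patients included in the study died from complications not associated with hypoglycemia". These are split by arm and cause. The first is described as "one in the physiological group secondary to progression of the infectious process, sepsis and septic shock". For the traditional arm the wording is "one in the group Traditionally associated with acute respiratory failure".

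Three other places bear on this:

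- Population characteristics: "The reasons for admission to the hospital were: abscesses and soft tissue infection, hip fracture, diabetic foot". Pneumonia comes later in the same list.
- Exclusion criteria: sepsis, septic shock and multiple organ failure are grounds for exclusion.
- Statistical analysis: the treatment analysis is to give the risk ratio and the absolute and relative risk reduction with 95% CI, for both the per-protocol and the intention-to-treat sets. Neither this section nor the procedures define a complication or say from when one counts.

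**The concern.** A safety outcome in a two-arm trial has to answer three questions: how many patients in each arm had an event, whether the event arose after treatment began, and whether like events were classified alike. As written, this outcome answers none of them for the events that occurred.

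Timing matters because an infection that brought the patient to hospital cannot be an effect of the insulin scheme. Localized infection is also a baseline factor in the starting-dose rules of both schemes, so infected patients were expected at entry. When the same condition is an admission diagnosis and the most frequent complication, the reader needs an onset rule to interpret it.

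Classification matters because the two fatal processes are handled differently and sit in different arms. With 36 and 39 patients, one patient moves an arm's rate by 1/36 = 2.8% or 1/39 = 2.6%, so one inconsistent entry is not trivial beside single-patient counts.

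**Working it through.** **1. Confirm the denominators on the outcome that is reported by arm.** Inputs, from Patients of the study and Safety results: 36 physiological and 39 traditional patients analysed by intention to treat; 15 in each with at least one hypoglycemia event.

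- RR = (15/36)/(15/39) = 1.083
- SE(log RR) = sqrt(1/15 - 1/36 + 1/15 - 1/39) = 0.283
- 95% CI = 1.083 × exp(±1.96 × 0.283) = 0.62 to 1.89; uncorrected chi-square p = 0.777

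This matches the stated 1.08 (0.62 to 1.89), p = 0.777.

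**2. Set out the complications by what is known.**

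| Item | Total | By arm | Reason for admission? |
|---|---|---|---|
| Soft tissue infection | not given | not given | yes |
| Pneumonia | 1 | not given | yes |
| Acute renal failure | 1 | not given | no (stage IV chronic kidney disease is listed, a different condition) |
| Acute respiratory failure | 1 | not given in the list | no |
| Bacteremia, ketoacidosis, hyperosmolar state | 0 | 0 v 0 | no |
| Sepsis and septic shock | not in the list | physiological, from the sentence on deaths | excluded at entry |

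Two of the four conditions that occurred overlap with admission diagnoses. One of the two fatal processes is in the list and one is not.

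**3. Bound what the missing split could hide.** These are ranges under stated assumptions, not estimates.

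- The three single-patient events, assuming three different patients: from 3/36 v 0/39 (+8.3 points, Fisher p = 0.11) to 0/36 v 3/39 (-7.7 points, p = 0.24).
- If the listed respiratory failure is the patient who died in the traditional arm, the upper end becomes 2/36 v 1/39 (5.6% - 2.6% = +3.0 points, p = 0.61).
- Soft tissue infection, with an assumed count and all cases in one arm: 4 v 0 gives Fisher p = 0.048; 0 v 6 gives p = 0.026.

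The missing split could point either way.

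**4. The deaths.** Taking both among the treated patients, 1/36 v 1/39:

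- RR = 1.083; SE(log RR) = sqrt(1 - 1/36 + 1 - 1/39) = 1.395
- 95% CI 0.07 to 16.7; Fisher p = 1.0

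The documents do not say whether the physiological-arm death was among the 36 who started insulin or was the 37th randomized patient, removed before insulin. With 1/37 the RR is 1.05 (0.07 to 16.2). Neither version favours a scheme.

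**The case against.** The strongest reply is that this is a narrow reporting gap. The trial was sized on hypoglycemia, which is compared by arm. The documents draw no conclusion about the schemes from complications. Three of the listed items are zero in both arms, deaths are fully reported, and a split table of rare events would be imprecise. All of that stands, and it limits the point to this one outcome. It does not explain why a named safety outcome has no arm counts when the analysis section plans risk ratios and absolute differences with intervals.

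A reader might infer more than the text supports:

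- *That admission infections were counted, pulling the arms together.* No section says so. The same category in two lists does not show the same episodes, since both infections can arise in hospital. No between-arm estimate was made, so none can have been biased.
- *That the fatal septic shock was left out of the report, favouring the physiological arm.* The next sentence reports it with its arm. That patient may also already be counted under an infection item, because the death is described as "secondary to progression of the infectious process, sepsis and septic shock". The defect is inconsistent classification, not concealment. The absence of bacteremia does not by itself contradict septic shock.
- *That the Secondary results section contradicts the list by reporting no adverse effects.* That statement concerns the use of insulin and does not deny complications.

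**Conclusion.** The point holds for this outcome only. For the complications that occurred, no comparison of the schemes can be made, for three reasons: there are no arm counts (and no count at all for the most frequent item), there is no onset rule although two of four conditions are also admission diagnoses, and the two fatal processes are classified differently.

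The size of any between-arm difference cannot be computed. The bounds above rest on assumptions: three different patients for the single events, and assumed counts for soft tissue infection. Treating septic shock as arising after entry rests on the exclusion criterion having been applied. Treating it as arising after the first insulin dose also requires that patient to be one of the 36 treated.

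The hypoglycemia comparison and the 1 v 1 split of deaths are unaffected. This should be corrected before anything is said about complications by scheme, but it does not alter a stated conclusion.

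**What to change.** 1. Define the outcome as a patient with at least one new or worsening complication after the first study insulin dose, and list the qualifying conditions.
2. Classify sepsis and septic shock by the same rule as acute respiratory failure. State whether the patient who died of septic shock had started study insulin.
3. Report patients by arm, n/36 v n/39 as analysed, in total and per condition, including the count for soft tissue infection. Give the risk ratio and absolute risk difference with 95% CI already planned in Statistical analysis. Where one arm has no event the risk ratio is undefined, so the absolute difference carries the result. Note that 37 patients were randomized to the physiological arm.
4. Tabulate infections present at admission by arm as a baseline characteristic.

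**Cost.** No new patients are needed, but onset dates have to be checked in the charts. Their availability is an assumption: the monitoring section describes glucose and HbA1c records, not complication dates. If dates cannot be recovered, give the arm counts and state that onset is unknown. The intervals will be wide because the trial was sized on hypoglycemia. That is a reason to print them, not to omit the comparison.

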There was a significant difference in the sustained control of blood glucose that was reported in 20 (55.6%) of the cases in the physiological group compared to 30 (76.9%) of the traditional group (per protocol, RR: 0.74, 95% CI: 0.58 to 0.94, $p = 0.009$; by intention to treat, RR: 0.72, 95% CI: 0.51 to 1.01, $p = 0.049$).

The causes of failure of the sustained control were discharge before control in goals, progress to critical state, death before glycemic control, poor adherence to the protocol and suspension for sustained hypoglycemia. With the "physiological" scheme it was necessary to suspend or change by another scheme in 8 (22.2%) patients, in comparison with the traditional scheme where only the scheme was suspended or changed in 1 (2.6%) patient (by intention to treat, RR: 8.67, 95% CI: 1.14 to 65.92, $p = 0.011$). There were no adverse effects to the use of insulin in both groups.

OTHER RESULTS

If the suspension of the scheme is considered for sustained hypoglycemia of 8 patients in the physiological group vs 1 patient in the control group, a risk ratio of 8.67 (95% CI: 1.14 to 65.9) and a number necessary to harm of 5.09 was calculated (95% CI: 2.93 to 19.23) patients with the physiological scheme to produce 1 event of hypoglycemia.

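### The sustained-control result is mostly the scheme suspensions counted again, so it is not separate evidence of less durable glucose control

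*Combined protocol and SAP*

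**What the plan says.** Secondary Results reports: "There was a significant difference in the sustained control of blood glucose that was reported in 20 (55.6%) of the cases" in the physiological arm, against 30 (76.9%) in the traditional arm. It prints RR 0.74 (0.58 to 0.94), p = 0.009 per protocol and RR 0.72 (0.51 to 1.01), p = 0.049 by ITT.

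The next sentence explains the failures: "The causes of failure of the sustained control were discharge before control in goals, progress to critical state, death before glycemic control", followed by "poor adherence to the protocol and suspension for sustained hypoglycemia". The section then gives suspension as a result of its own: in the physiological arm "it was necessary to suspend or change by another scheme in 8 (22.2%) patients", against 1 (2.6%) in the traditional arm, RR 8.67 (1.14 to 65.92). Other Results uses the same 8 v 1 again for a number needed to harm of 5.09.

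Patients of the Study describes a different quantity with the same counts: "In 20 (71.4%) patients in the first group and in 30 (96.8%) patients in the second group, treatment was completed until discharge". It also lists who left before the per-protocol analysis. For the physiological arm: "6 patients did not conclude the treatment by discharge before the control and 2 patients due to poor adherence". For the other arm: "In the traditional group, 5 patients withdrew before the control, 1 patient due to poor adherence to treatment", then "1 patient died before the control, and 1 patient was suspended due to critical condition".

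Nothing from Material and Method through Statistical Analysis defines sustained control by a glucose threshold, a duration or anything else.

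**The concern.** The label suggests that glucose, once controlled, stayed controlled more often under the traditional scheme. The listed causes of failure do not measure that. None is a later loss of control through high glucose. They are leaving before control, clinical deterioration, death, poor adherence and stopping the scheme for hypoglycaemia.

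If suspension is one of the ways to fail, and suspensions are then reported as a second result and again as a number needed to harm, the same patients appear three times. A reader would count an efficacy loss plus a safety signal. At stake is what the trial can say about efficacy. The suspension signal itself is not in doubt here.

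**Working it through.** **Inputs.** ITT 36 v 39, per protocol 28 v 31, early exits and treatment completed to discharge (20 v 30): Patients of the Study. Sustained control (20 v 30) and suspensions (8 v 1): Secondary Results. Deaths: Safety Results.

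**1. Reproduce the printed figures.** RR = (a/n)/(b/m), with 95% CI = RR × exp(±1.96 × √(1/a − 1/n + 1/b − 1/m)).

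- ITT, 20/36 v 30/39: 0.5556/0.7692 = 0.722; √0.0299 = 0.173; CI 0.515 to 1.014. Pearson χ² = 4² × (1/12 + 1/13 + 1/24 + 1/26) = 3.846, p = 0.0499. The smallest expected count is 12, so chi-square is the test that Statistical Analysis calls for.
- Per protocol, 20/28 v 30/31: RR 0.738 (0.579 to 0.941). The smallest expected count is 4.27; Fisher p = 0.0098.
- Suspensions, 8/36 v 1/39: RR 8.667 (1.139 to 65.92). Risk difference 0.1966; 1/0.1966 = 5.09.

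All match the document, with p values truncated to three decimals.

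**2. Identify the outcome.** The per-protocol RR for sustained control is reproduced by the table for treatment completed to discharge (20/28 v 30/31). Failures also include discharge or death before control. Together these fit one composite: reached control and stayed on the assigned scheme to discharge.

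**3. Close the counts.**

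| | Physiological | Traditional |
|---|---|---|
| ITT | 36 | 39 |
| Left before per-protocol analysis | 6 + 2 = 8 | 5 + 1 + 1 + 1 = 8 |
| Per protocol | 28 | 31 |
| Later failures | 28 − 20 = 8 | 31 − 30 = 1 |
| Success | 20 | 30 |

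The later failures, 8 v 1, match the reported suspensions in number.

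**4. Split the ITT difference.**

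- Total: 30/39 − 20/36 = 21.4 points (risk difference −21.4, 95% CI −42.3 to −0.4).
- Suspensions: 8/36 − 1/39 = 19.7 points; 19.66/21.37 = 92%.
- Remaining failures: 8/36 − 8/39 = 1.7 points (−16.9 to 20.3).
- Nearest available proxy for reaching control, 28/36 v 31/39: RR 0.98 (0.77 to 1.24).

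**5. Vary the two unreconciled patients.** The physiological-arm death is not among that arm's listed exits, so it may be one of the 8 later failures. The traditional patient stopped because of a critical state is not reconciled with the single traditional suspension.

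| Suspensions counted | Assumption | Points | Share of 21.37 |
|---|---|---|---|
| 8 v 1 | as reported | 19.7 | 92% |
| 8 v 2 | critical-state patient is a further suspension | 17.1 | 80% |
| 7 v 1 | one later physiological failure is not a suspension | 16.9 | 79% |
| 7 v 2 | both of the above | 14.3 | 67% |
| 8 v 0 | the one traditional suspension is the critical-state patient, not a hypoglycaemia case | 22.2 | 104% |
| 7 v 0 | the same, and one later physiological failure is not a suspension | 19.4 | 91% |

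At 67%, the remaining failures are 9/36 v 7/39: 7.1 points, p = 0.46.

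**6. Fragility.** Moving one physiological patient to success (21/36 v 30/39) gives Pearson p = 0.085.

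**7. Neighbouring p values.** Effectiveness Results prints fasting p = 0.114 and morning p = 0.081 identically for both analysis sets, although the means differ. t tests from the printed means and SDs give fasting 0.32 (ITT) and 0.45 (per protocol), and morning 0.12 and 0.41. The postprandial values do reproduce: 0.902 by ITT, and 0.835 (Welch 0.834) against a printed 0.833 per protocol. A rank test could explain a gap, but not readily the same p in both sets. The argument above does not use these p values.

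**The case against.** **Hypoglycaemia is also loss of control.** If control is two-sided, a scheme stopped for repeated low readings did fail to sustain it, and the label is defensible. This stands as a defence of the composite. It does not make the result separate from the suspensions.

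**The composition is disclosed.** The causes of failure follow directly, and Other Results ties its number needed to harm to the same 8 v 1. That is fair. But the text never says that the results share patients, and it leaves the claim as an unqualified significant difference in glucose control.

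**The 67% is not a true bound.** The section reports 8 v 1. If all of those are failures, their share is 92% whoever they are; the other rows replace the reported count with a different one. This is correct. Those rows show sensitivity to the two unreconciled patients, and the 67% only makes the statement more cautious. Lower shares can be built (6 v 2 gives 54%), but they need suspensions to overlap the poor-adherence exits and leave a per-protocol failure without a reported cause.

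**The remaining difference is imprecise.** Its interval of −16.9 to 20.3 cannot exclude a gap nearly as large as the whole effect. This stands. The shares describe the reported counts and do not show that the arms are equal apart from suspensions.

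**The definition may sit elsewhere.** The available text has no outcomes section, so this cannot be excluded, and the definition should be confirmed before relabelling.

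**Hypoglycaemia counts bear on the overlap.** The per-protocol RR of 7.75 (1.02 to 59.13) in Safety Results for more than two events reproduces as 7/28 v 1/31. That is close to the 8 v 1 later failures and consistent with the inferred overlap, but it does not identify the patients.

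**Conclusion.** The concern holds. On the reported counts, 92% of the ITT difference in sustained control (19.7 of 21.4 points) is the suspensions that the document reports separately, and 67% on the least favourable reading in the table. Per protocol, all later failures match the suspensions in number (8/28 v 1/31, the whole 25.3 points). The result should not be read as evidence of less durable glucose control in addition to the suspension finding, and the ITT comparison is borderline.

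This rests on two inferences: that the outcome is the composite described, and that the 8 v 1 later failures are the 8 v 1 suspensions. Identical numerators, exact closure of the counts and the listed causes support both, but only patient-level data can confirm them. Counting suspension for hypoglycaemia as failure is defensible. The faults are the label, the unqualified claim, and the missing statement that the results share patients. It should be fixed; the arithmetic of the printed result is sound.

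**What to change.** 1. Confirm the definition against patient-level data, then rename the outcome as reaching control and remaining on the assigned scheme to discharge.
2. Tabulate reaching control in all ITT patients separately from suspension or change of scheme (8/36 v 1/39). State that the composite includes the suspensions, and do not present the two as independent findings.
3. Give one cause for each of the 16 v 9 ITT failures. Reconcile the physiological-arm death and the traditional critical-state patient with the 8 v 1 count.
4. Describe the ITT result as borderline: RR 0.72 (0.51 to 1.01), Pearson p = 0.0499, risk difference −21.4 points (−42.3 to −0.4), alongside the per-protocol RR 0.74 (0.58 to 0.94).
5. Before citing mean-glucose p values beside this result, recheck 0.114 and 0.081 in both analysis sets and name the test used.

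The cost is re-tabulation of existing data and some rewording; no new data are needed. A claimed significant glucose-control result becomes a borderline composite driven mainly by suspensions. The safety and tolerability signal is unchanged.
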